6. RESEARCH QUESTION AND OBJECTIVE(S)

This study aims to:

- i) gain an understanding of the clinical management of complicated influenza in ICU in Europe, including treatment patterns, monitoring the entry of new anti-influenza treatments and utilisation of diagnostic tests including resistance testing.
- ii) investigate the clinical effectiveness of IV zanamivir treatment in ICU patients with complicated influenza illness. Specifically:

Primary objective:

- To compare all-cause in-hospital mortality in a group of ICU-admitted patients with complicated influenza who receive treatment with IV zanamivir as part of their clinical care with all-cause in-hospital mortality in a propensity score-matched group of ICU patients who did not receive this therapy during the same influenza seasons and/or pandemic(s).

Secondary objectives:

- To understand, through the analysis of historical data, treatment patterns for ICU-admitted influenza patients and factors associated with NAI treatment.
- To estimate, in a time-dependent manner, the crude IV zanamivir treatment effect on all-cause in-hospital mortality in a group of ICU-admitted patients with influenza.
- To compare all-cause in-hospital mortality at 7, 10 and 14 days after IV zanamivir treatment initiation/matching in the two groups.

Exploratory objectives:

- To explore, through inverse-probability of censoring weighting (IPCW) analysis, the effect of non-persistence to exposure status in the analysis of the primary objective, above.
- To define the clinical course of disease for the IV zanamivir and comparator groups, categorized in 6 categories on an ordinal scale as described in Section 7.3.2.
 - The category of each patient on day 7, 10, 14 after IV zanamivir treatment initiation/matching
 - The change in category over time of each patient, from Day 1 to Day 14 after IV zanamivir treatment initiation/matching
- To compare the length of hospitalisation between the two groups
- To compare the length of ICU stay between the two groups
- To summarize associated complications of influenza (bacterial pneumonia, sepsis, myocarditis, encephalitis, acute respiratory distress syndrome, respiratory failure, bronchitis) in both groups.

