7.6.3. Timings of Assessment during follow-up

The final data collection time for both the historical and comparative cohorts of the study is at hospital discharge, the latest available date before study withdrawal or loss to follow-up, or at day 28 after hospital admission if a patient has not been discharged or has been re-admitted to hospital within the 28-day study period.

The dedicated research nurse(s) at each site will check medical charts of discharged patients to identify eligible patients. [Table 2](#) below outlines for which times each (group of) variable(s) of interest will be collected.

Table 2 Proposed exposure and outcome assessment intervals

Data variable	At hospital admission	Before ICU admission	At/after ICU admission	Hospital discharge OR Day 28 post-treatment
Demographics	X			
Influenza diagnostics/details (e.g. influenza strain/type, diagnostic test)	X			
Other risk factors (confounders/effect modifiers from Section 7.3.3)	X	X	X	
In-patient IV zanamivir treatment	X	X	X	X
Admission to critical care facilities (e.g. ICU/high dependency unit [HDU])	X		X	X
Ordinal scale clinical outcomes	X	X	X	X
Mortality in hospital		X	X	X

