7.7. Data analysis

7.7.1. Essential analysis

All analyses will be performed in SAS 9.4. Descriptive analyses will be performed with continuous variables expressed as means with 95% confidence intervals or medians and ranges, as appropriate for the data distribution. Categorical variables will be expressed as frequency or proportion of patients in each category.

The sub-sections below are an outline of the types of analyses that are currently being considered. A detailed statistical analysis plan will be written before data collection for the comparative cohort starts.

PART I: Historical Cohort

A logistic regression analysis will be performed to identify factors associated with anti-influenza treatment versus no anti-influenza treatment. If sufficient data are available, the analysis will be repeated for IV zanamivir.

PART II: Comparative Cohort

Propensity scores will be derived from the predicted probability of IV zanamivir treatment estimated in a multivariable pooled logistic regression model with treatment/no treatment fitted as the binary outcome and the covariates listed in Section 7.3.3 above specified as explanatory variables. Treatment and exposure data will be captured separately for the pre- and post-ICU periods as per Section 7.6.3, and models will be stratified by season (to control for differences in severity) and by time since illness onset to facilitate appropriate matching. Standardised differences will be calculated to assess the balance achieved in the matched sample [Austin, 2011a]. If an insufficient number of matched pairs are obtained, alternative approaches e.g. propensity score stratification or inverse-probability of treatment weighting (IPTW) will be considered and the analysis modified accordingly [Cullen, 2009; Austin, 2011a]. Similarly, if only a small number of patients are exposed to IV zanamivir then a Disease Risk Score-match approach will be applied [Glynn, 2012]. For analysis of within-hospital mortality fitted as the binary outcome, the same method will be applied.

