If there are sufficient data, propensity score-matched samples will be created to compare: early (≤ 2 days from symptom onset to treatment initiation) versus late IV zanamivir treatment (> 2 days from symptom onset to treatment initiation); early IV zanamivir treatment versus no treatment; late IV zanamivir treatment versus no treatment. Analyses will also be conducted in the subset of mechanically-ventilated patients, and, if sufficient data are available, an analysis will be conducted on patients infected with influenza viruses where resistance is confirmed. If numbers are sufficient, further stratified analyses will be performed for adults and children (aged < 16 years) as well as for immunocompromised patients.

Following matching, patients will accrue time-at-risk from ICU admission (for IV zanamivir patients who initiated prior to ICU admission), treatment initiation (for IV zanamivir patients who initiated in the ICU) or ICU admission (comparator patients); as the study is conducted among ICU-admitted patients, person-time prior to ICU admission is immortal. Patients will be followed up until they experience the event of interest (death) or they are censored (the earlier of hospital discharge or 28 days post treatment/matching [as applicable]). For the secondary objectives described below censoring will be modified as appropriate (7, 10 or 14 days post treatment/matching).

Primary objective: all-cause in-hospital mortality to end of follow-up

A matched Cox regression analysis will be performed to estimate the association between IV zanamivir treatment and mortality during hospital stay. The treated vs. untreated groups will be compared to obtain the hazard ratio for in-hospital survival. Kaplan-Meier plots will be produced for graphical comparison of survival in the two groups.

Secondary objective: crude all-cause in-hospital mortality to end of follow-up

A crude estimate of the hazard ratio, based on the unmatched sample, will also be obtained using a time-dependent Cox regression model stratified by season, to control for differences in severity.

Secondary objective: All-cause in-hospital mortality at Day 7, 10 and 14

A regression analysis, similar to the primary analysis, will be performed on available mortality data at Day 7, 10 and 14 post treatment/matching.

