7.7.2. Exploratory analysis

Inverse Probability of Censoring Weighted (IPCW) Analysis

The proposed matching strategy seeks to minimise bias by not utilising future information to define exposure status [Hernan, 2016]. Accordingly, patients who are matched as controls may go on to receive IV zanamivir and treated patients may discontinue IV zanamivir. To examine the effect of this potential exposure misclassification, if observed to some ($\geq 10\%$) degree, (IPCW) analysis will be performed for the primary objective analysis. Patients who do not persist to their exposure status will be censored at the time of non-persistence, and stabilised weights – generated from a pooled logistic regression model with non-persistence fitted as the outcome variable and the parameters described in Section 7.3.3 included as explanatory variables – will be utilised in a weighted pooled logistic regression analysis of the effect of IV zanamivir treatment on all-cause within-hospital mortality.

Ordinal Scale at Day 7, 10 and 14

A proportional odds regression model will be fitted to estimate the odds of different categories of the ordinal scale at Day 7, 10 and 14, and their 95% confidence intervals, in the IV zanamivir group compared with the untreated group. Results will be presented for two levels of adjustment: (i) unadjusted (i.e., crude comparison) and (ii) using propensity score stratification with additional adjustment for ICU ventilation on Day 1, inpatient antibiotics and systemic corticosteroids. Patients will be assigned to the point on the ordinal scale based on the information for that day and not for the period up to and including that day (e.g. 0-7, 0-10, 0-14 days).

Length of hospital/ICU admission

Matched t-tests, or alternative non-parametric tests, will be performed to compare length of hospital stay and length of ICU admission between IV zanamivir and no IV zanamivir treatment patients (and, if sufficient data exist, by early/late treatment).

Associated complications

Descriptive analyses of the proportion of each treatment group with associated complications of influenza (bacterial pneumonia, myocarditis, encephalitis, sepsis, acute respiratory distress syndrome, respiratory failure, bronchitis) during ICU stay will also be reported.

For optimal comparability, the primary and secondary analyses will be repeated using the following definitions, which are similar to what was used in the Phase 3 clinical trial:

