7.7.3. General considerations for data analyses

Missing data

It is anticipated that missing data will be minimal given the source of the information on patients (e.g. medical chart review). Accordingly, missing data will be recorded as such (e.g. coded as 99), but with those records retained (e.g. propensity score calculations) or excluded (e.g. T tests to compare admission/ICU length) as appropriate. Patients for whom details on potential risk factors are missing will not be included in the sensitivity analyses.

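### Length of stay is compared by t-tests or rank tests that do not handle deaths or stays unfinished at day 28, so the result mixes mortality with recovery and can be biased either way

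*Protocol*

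**What the plan says.** Among the exploratory objectives in Protocol section 6 is "To compare the length of hospitalisation between the two groups", with a matching objective for ICU stay. Both concern the whole groups, not survivors. Section 7.7.2 names the method: "Matched t-tests, or alternative non-parametric tests, will be performed to compare length of hospital stay and length of ICU admission".

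Two other sections bear on which days enter.

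- Section 7.7.3 lets records with missing data be "excluded (e.g. T tests to compare admission/ICU length) as appropriate". It mentions no other exclusion for these tests.
- Section 7.6.3 ends data collection at hospital discharge, "or at day 28 after hospital admission if a patient has not been discharged or has been re-admitted to hospital" within the study period. Table 2 in that section instead labels its last column as discharge or day 28 after treatment. Section 7.7.1 censors the survival analysis at "the earlier of hospital discharge or 28 days post treatment/matching [as applicable".

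No passage says how an in-hospital death, or a stay still running at day 28, enters the length-of-stay comparison. None gives the day from which stay is counted.

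**The concern.** A hospital stay in this study ends in one of three ways: discharge alive, death, or the day-28 end of data collection. A t-test or ordinary rank test on days of stay does not distinguish them. A patient who dies in hospital has a complete, observed stay, so the missing-data exclusion does not remove it. Followed as written, the comparison gives a death on day 5 the same value as a discharge on day 5.

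This sits badly with the Protocol's own ordinal scale in section 7.3.2, which places discharge in the best category and death in the worst. The study is designed to detect a mortality difference. Such a difference moves mean stay even when no patient recovers faster or slower, so a reader could take a mortality effect for an effect on recovery, in the wrong direction.

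**Working it through.** **Inputs from the Protocol (section 7.5).** Untreated mortality 12% in the planning case, range 5% to 25%; odds ratio 0.5; α = 0.05; 80% power; continuity correction; 450 per arm at 12% and 233 per arm at 25% (Table 1, 1:1).

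**Assumptions.** The Protocol gives no stay lengths. All stay lengths below are assumed and varied.

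**Step 1: the plan's own figure.** Treated odds = 0.5 × 0.12/0.88 = 0.0682, so treated mortality = 0.0682/1.0682 = 6.38%. The two-sided, continuity-corrected formula for two proportions gives 449 per arm against 450 stated, so the planning rates are read correctly. At 25%, treated mortality is 14.29%.

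**Step 2: shift in mean stay with no effect on recovery.** Assume mean stays of 14 days (survivors) and 7 days (non-survivors) in both arms.

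- Untreated: 0.12 × 7 + 0.88 × 14 = 13.16 days
- Treated: 0.0638 × 7 + 0.9362 × 14 = 13.55 days
- Difference: +0.39 day

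In general the difference is (0.12 − 0.0638) × (survivor stay − non-survivor stay) = 0.0562 × gap. Survivors 12 and non-survivors 10 give 0.0562 × 2 = 0.11. Survivors 16 and non-survivors 7 give 0.0562 × 9 = 0.51.

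**Step 3: simulation with the day-28 cap.** Lognormal stays (log SD 0.7), stays capped at 28 days, odds ratio 0.5, deaths entered at their observed stay, 2,000 replicates, and an unpaired t-test as an approximation to the matched one. Entries are treated minus untreated mean days; brackets give the share of runs significantly longer under treatment.

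| Assumed median days (death / discharge) | 12%, 450 per arm | 25%, 233 per arm |
|---|---|---|
| 7 / 14 | +0.39 (10%) | +0.73 (15%) |
| 7 / 14, saved patients stay 1.5 times as long | +0.63 (21%) | +1.20 (35%) |
| 5 / 18, saved patients stay 1.5 times as long (extreme) | +0.90 (36%) | +1.70 (54%) |
| 14 / 14 | 0.00 (2.6%) | not run |
| 20 / 14 | −0.21 (1.1%) | −0.41 (0.9%) |
| As row 2, but treated survivors' stays truly 10% shorter | −0.45 (0.3%) | +0.22 (4.8%) |

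The +0.39 in row 1 agrees with Step 2 partly by coincidence: Step 2 uses means without a cap, and row 1 uses medians with one. In the last row the drug does speed recovery, yet at 25% mortality the raw comparison still points to a longer stay.

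**Step 4: the cap on its own.** In row 1 at 12% about 14% of untreated stays run past day 28. Capping them moves the difference from +0.51 to +0.39 in row 1, from +1.01 to +0.63 in row 2, and from −0.41 to −0.21 in row 5 (all at 12%). It pulls the difference towards zero whichever sign it has.

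**Step 5: the death rule.** In row 1 at 12%, giving deaths the worst value of 28 days instead of their observed stay changes +0.39 to −0.69, so the rule alone decides the sign. Restricting to survivors gives about 0 in row 1, but +0.26 (12%) and +0.55 (25%) in row 2, because saved patients join the treated survivors. Dropping deaths is therefore not a clean solution.

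**The case against.** The strongest reply is that the Protocol does not state a death rule at all, that section 7.7.1 introduces its analyses with "The sub-sections below are an outline of the types of analyses that are currently being considered", and that a detailed statistical analysis plan is to follow. A stay with no discharge date might be excluded as missing rather than scored 28. The objective is exploratory, and the ordinal scale at Days 7, 10 and 14 already assesses recovery with death included.

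Much of this stands. It keeps the point small and leaves the treatment of unfinished stays open. It does not remove the point, because the Protocol does name the tests, applies them to whole groups, and mentions no exclusion that would catch a death. Detail added later to a t-test or rank test on raw days does not make it suitable; a rank test would serve only if death had a stated rank.

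Two stronger readings are tempting and unsupported. A reader might infer that a life-saving drug will appear to prolong hospitalisation. That needs deaths to come earlier than discharges and no offsetting effect on survivors' stay, and the Protocol gives no stay lengths from which to establish either. A reader might also infer that the day-28 cut-off helps to create the apparent prolongation. In the runs it reduced it.

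**Conclusion.** The named tests are unsuited to this outcome. Followed as written, they mix mortality with recovery time, and the bias can have either sign. At the planning mortality of 12% against 6.4%, with deaths earlier than discharges, it is about +0.4 day (0.11 to 0.51 over the simple range of assumed stays), and below 1 day in every 12% case run. At 25% mortality it reaches +0.73 day, or +1.20 if saved patients stay 1.5 times as long. It is zero when deaths are as late as discharges, and negative when they are later. Truncation at day 28 is a separate defect that shrinks differences.

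These sizes rest on assumed stays and on deaths entering at their observed stay, which the text implies by default but does not state. The primary mortality analysis is unaffected. The change is worth making before comparative data collection, since a length-of-stay result that seems to contradict a mortality benefit would be hard to explain afterwards.

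**What to change.** First reconcile the day-28 origin: hospital admission in the text of section 7.6.3, treatment in its Table 2, and treatment or matching in section 7.7.1. This decides whether the data for the chosen horizon exist. For example, if the index date falls 5 days after admission, collection that stops 28 days after admission covers only 28 − 5 = 23 days from index.

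Then replace the tests on raw days with one of these:

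- time from the index date to discharge alive, and to ICU discharge alive, with death as a competing event (cumulative incidence, Fine-Gray) and administrative censoring at day 28; or
- hospital-free and ICU-free days to day 28, with death scored 0.

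Both still respond to mortality, but in a declared direction in which death never counts as a good result. Starting at the index date also keeps pre-treatment days out of the comparison, a question the Protocol leaves open by giving no origin for stay. Show observed days only descriptively, separately for survivors and non-survivors.

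The cost is wording and programming for an exploratory analysis, and a summary less familiar than mean days. No further data are needed if the horizon is day 28 after admission. A horizon of 28 days from index needs the collection window to match.

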7.2. Study Population and Setting

Study population

PART I: Historical Cohort

Inclusion criteria:

- Adults, adolescents, children and infants of all ages who were admitted to ICU with influenza illness.

Exclusion criteria:

- No informed consent given in countries where informed consent for retrospective chart reviews is mandated by local ethics/regulatory requirements.
- Prior treatment (within 30 days) with an investigational influenza drug therapy.

PART II: Comparative Cohort

Inclusion criteria:

- Adults, adolescents, children and infants of all ages who were admitted to ICU with influenza illness and treated with IV zanamivir as part of their routine medical care, treated with inactive antivirals or not treated at all.
 - Treatment may be initiated before or during ICU admission

Exclusion criteria:

- No informed consent given in countries where informed consent for retrospective chart reviews is mandated by local ethics/regulatory requirements.
- Prior treatment (within 30 days) with an investigational influenza drug therapy.

Setting

Hospitals are eligible to participate in this study if they fulfil all of the following criteria:

- Tertiary centre with ICU
- Ability to provide the variables of interest as described in Section 7.3.
- Ability for in-house testing for influenza type and sub-type by approved diagnostics

Hospitals in the European Union, UK, Norway and Iceland that participated in the Phase II and Phase III clinical trials, and the compassionate use program that meet the above criteria may be invited to join this study. These sites are situated in Belgium, the Czech Republic, Denmark, France, Germany, Greece, Hungary, Latvia, the Netherlands, Norway, Poland, Portugal, Slovakia, Spain and the UK. Additionally, ICU networks in France, Italy and the UK were identified through a literature search. A brief description of the networks can be found in the table below. If necessary, further hospitals will be identified through existing hospital networks that were set up for influenza surveillance or for post-pandemic data analyses. In the same literature review, networks in Spain [Cuevas Gonzalez-Nicolas, 2010] and the UK [Nguyen-Van-Tam, 2010] were identified as potentially interesting for follow-up.

Country	Network	Description
France	REVA-SRLF [Richard, 2012]	Network of 89 ICUs (25% of all ICUs in France) that reported ICU admissions (influenza vs non-influenza)

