7.3.3. Confounders and effect modifiers

Outcomes will be summarised according to the following risk factors:

- Season/pandemic
- Country/centre
- Influenza strain/sub-type
- Age
- Sex
- Body mass index (BMI)
- Smoking status (Current, ex- smoker, never smoked)
- Vaccination status, other antiviral treatments, antibiotics
- Underlying co-morbidities including but not limited to:
 - Asthma
 - Chronic obstructive pulmonary disease (COPD)
 - Other pulmonary diseases
 - Other chronic conditions (e.g. Cardiovascular Disease, Chronic Kidney Disease, Diabetes, Neurological Disease and Obesity)
 - Immunocompromised
 - Pregnancy
 - Obesity
 - Prematurity
- Co-infecting viruses
- Duration of flu-specific symptoms prior to hospitalisation/treatment
- Presentation at admission (Influenza-like illness [ILI], pneumonia, otitis media [OM], sepsis etc.)
- Requiring supplemental oxygen
- Mechanical ventilation in ICU
- Days from hospital admission to ICU/critical care admission
- In-hospital corticosteroid administration (timing, drug, dose, frequency etc.)
- In-hospital antibiotic administration (timing, drug, dose, frequency etc.)
- Reason why patient has limited treatment options

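### The complications table counts events over the ICU stay, not from the start of time-at-risk, so it includes pre-dose events in patients who start IV zanamivir in the ICU and omits events after ICU step-down in both groups

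*Protocol*

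**What the plan says.** Section 7.7.2 (Associated complications) plans "Descriptive analyses of the proportion of each treatment group with associated complications of influenza" and fixes the counting window at the end of the same sentence: "acute respiratory distress syndrome, respiratory failure, bronchitis) during ICU stay will also be reported". It sets no condition on when the complication began relative to treatment or matching.

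Other sections bear on that window:

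- Section 7.2 (Part II inclusion): "Treatment may be initiated before or during ICU admission".
- Section 7.7.1 (start of time-at-risk): patients treated before ICU start at ICU admission. For the rest the start is "treatment initiation (for IV zanamivir patients who initiated in the ICU) or ICU admission (comparator patients").
- Section 7.7.1 (end of follow-up): death or censoring, the latter at "the earlier of hospital discharge or 28 days post treatment/matching [as applicable"].
- Section 6 (exploratory objectives): "To summarize associated complications of influenza" in both groups, without restriction to the ICU. The exploratory outcome list in section 7.3.2 has no such restriction either.
- Section 7.3.3 (covariates): "Presentation at admission (Influenza-like illness [ILI], pneumonia, otitis media [OM], sepsis etc".)
- Section 7.6.3, Table 2: no row names complications or their onset.

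**The concern.** The mortality analysis has a deliberate time origin, chosen so that each patient's time-at-risk begins at a defensible point. The complications table uses a different window, tied to ICU entry and exit. For a patient whose first dose comes some days into the ICU stay, that window opens before the exposure. A complication that led to treatment is then tabulated in the same way as one that followed it.

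The window also closes at ICU discharge, so it drops later events that the study's own follow-up would otherwise capture. A side-by-side table by treatment group invites a comparative reading, and section 10.1 names the regulators as the primary audience. A table that mixes reasons for treatment with later events cannot be read safely in either direction.

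**Working it through.** The protocol states no complication rate, so there is no figure to reproduce. The check sets the complication window against the section 7.7.1 risk period, then illustrates the consequence on assumed inputs.

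**Step 1. The two windows compared.**

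| Patients | Time-at-risk starts (7.7.1) | Complication window opens (7.7.2) | Result |
|---|---|---|---|
| IV zanamivir started in ICU | First dose | ICU admission | Pre-dose ICU events counted as treated-group events |
| IV zanamivir started before ICU | ICU admission | ICU admission | Starts agree |
| Comparators | ICU admission | ICU admission | Starts agree |
| All | (ends at hospital discharge or 28 days) | (closes at ICU discharge) | Events after step-down not counted |

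The ICU time before the start of time-at-risk therefore enters the treated arm only, and only through in-ICU starters. The loss after step-down applies to both arms.

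**Step 2. Effect on a reported proportion.** Call the section 7.7.1 start of time-at-risk the index time. Assumed quantities:

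- *a*: share of a group with a complication already present at the index time and counted by the ICU window.
- *p*: new onset after the index time in comparators.
- *r*: true risk ratio after the index time.

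Reported proportion in the treated group: *a* + (1 − *a*) × *p* × *r*. For comparators set *r* = 1.

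*Equal prior share, p = 20%, r = 0.5:*

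- *a* = 10%: 0.10 + 0.90 × 0.10 = 0.190 against 0.10 + 0.90 × 0.20 = 0.280; ratio 0.68.
- *a* = 30%: 0.30 + 0.70 × 0.10 = 0.370 against 0.30 + 0.70 × 0.20 = 0.440; ratio 0.84.
- *a* = 50%: 0.50 + 0.50 × 0.10 = 0.550 against 0.50 + 0.50 × 0.20 = 0.600; ratio 0.92.

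A halving of risk is diluted towards no difference.

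*Unequal prior share, p = 20%, r = 1 (no drug effect):*

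- 30% against 20%: 0.440 / 0.360 = 1.22.
- 50% against 30%: 0.600 / 0.440 = 1.36.
- 50% against 10%: 0.600 / 0.280 = 2.14.

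As a difference, with *p* = 15% and prior shares of 35% and 20%: 0.35 + 0.65 × 0.15 = 0.4475 against 0.20 + 0.80 × 0.15 = 0.32, an apparent excess of 12.75 percentage points with no drug effect.

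*Equal prior share, r = 1:* with 35% in both groups and *p* = 15%, both report 0.4475 and the difference is zero.

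**Step 3. What counting from the index time does.** Among patients free of the complication at the index time, the proportions are *p* × *r* and *p*. Their ratio is *r* in every scenario above.

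**The case against.** The strongest reply is that this is a descriptive, exploratory table. Section 6 uses the verb compare for length of stay but only summarise for complications, and no test, model or effect estimate is attached. That stands. A reader might infer that the protocol attributes pre-dose events to the drug, but no attribution is planned.

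A reader might also infer that the table will show an excess on IV zanamivir even if the drug does nothing. The protocol does not support this as a certainty. Section 7.7.1 plans propensity matching on the section 7.3.3 covariates, which include presentation at admission, supplemental oxygen and mechanical ventilation, with standardised differences checked. With equal prior shares and no effect, the difference is zero. A false excess needs residual imbalance. Section 7.9 recognises that treated patients may be sicker, which makes the direction plausible but does not give its size.

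Three further inferences go too far:

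- *That ward complications before ICU transfer are wrongly omitted.* Section 7.7.1 starts time-at-risk at ICU admission for patients treated earlier, because the time before it is immortal. Leaving those events out agrees with that rule.
- *That one episode will serve as both covariate and outcome.* Pneumonia and sepsis appear among the admission presentations, and bacterial pneumonia and sepsis among the complications. Nothing says an admission diagnosis will be recounted; the protocol only lacks a rule to prevent it.
- *That onset dates will not be collected.* Table 2 is headed as proposed and groups variables. A missing row does not show that the eCRF lacks the field.

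Finally, it can be said that section 7.7.1 describes its analyses as an outline and that a detailed SAP will follow. That would answer an unstated detail. Here the protocol itself states a window, and the SAP would have to depart from it.

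**Conclusion.** The point holds for one exploratory table. As written, section 7.7.2 counts pre-dose ICU complications for in-ICU starters in the treated group, and it loses complications after step-down in both groups. The window disagrees with the section 7.7.1 risk period and is narrower than the objective in section 6 and the outcome in section 7.3.2. The primary and secondary mortality analyses are not touched.

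The size cannot be derived from the protocol. It depends on how many patients start in the ICU, how often complications precede the first dose, and how well matching balances them. The ratios above are illustrations on assumed rates. They show that the window can dilute a true difference, or create an excess if imbalance remains.

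**What to change.** In section 7.7.2, replace the ICU-stay limit with onset after the start of time-at-risk defined in section 7.7.1 (ICU admission for pre-ICU starters and comparators, treatment initiation for in-ICU starters), up to the section 7.7.1 end of follow-up. Tabulate complications already present at that start separately, as baseline. List ward events after first dose in pre-ICU starters separately too. Counting from first dose in all treated patients would add pre-ICU events to the treated arm only, because comparators contribute no time before ICU admission.

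Add complication and onset date as a row in Table 2 and a field in the eCRF. Without the date, prior and new events cannot be separated later.

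The cost is one sentence, one table row and one eCRF field. The downside is that some onset dates abstracted from charts will be approximate.
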